B.1.3. Study of HCV treatment in methadone patients. In 2003, we adapted our on-site multidisciplinary HCV program to include directly-administered weekly pegylated IFN in addition to screening, assessment of treatment eligibility, psychiatric services, and on-site antiviral therapy. Of 73 patients, most were Latino (67%) or African-American (12%), nearly half (49%) had used illicit substances in the 6 months before initiating treatment, 32% were HIV-infected, and current psychiatric illness was common (67%). Most (86%) completed 12 weeks of HCV treatment and 45% achieved SVR, including 40% of genotype-1 patients. Though 30% used illicit drugs during HCV treatment, there was no association between illicit drug use and virological outcomes. These results demonstrate that IDUs with complex medical and psychiatric comorbidities can be effectively treated for HCV with co-located on-site care. However, it is unknown which interventions (multidisciplinary on-site care v. DOT injections) contributed to the observed outcomes.

B.1.4. Pilot RCT of directly observed HCV treatment in methadone patients. In 2008 we began a pilot RCT (K23 DA022454, PI: [name]) of modified DOT (mDOT) which extended our DOT strategy to the oral medication ribavirin. We designed this trial to test the efficacy of 2 versions of mDOT. Our primary objective was to determine whether enhanced DOT with both IFN plus ribavirin is more efficacious than standard DOT with weekly provider-administered IFN and self-administered ribavirin for improving adherence. We have completed the study (n=80), and we observed significant differences in pill count adherence between the treatment arms (88% in mDOT arm vs. 77% in the treatment as usual, $p=0.02$). In addition, 81% of patients in the mDOT arm achieved SVR, compared to 61% in the treatment as usual arm. **ENSTEIN** IRB NUMBER: 2016-7215 IRB APPROVAL DATE: 02/18/2018

of mDOT subjects achieved $\geq 80\%$ adherence v. 53% in the TAU arm ($p=0.09$). Only 16% discontinued treatment, and among genotype-1 infected patients, 55% achieved SVR (half active drug users). We have an ongoing NIH-funded study of all-oral HCV treatment delivered by DOT at the methadone program; SVR has exceeded 80% with sofosbuvir-based regimens in combination with ribavirin (with and without IFN).

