Adherence to Zepatier (continuous measure) will be determined as the amount of medication taken by each patient during the first 12 weeks will be expressed as a percentage (with a 0-100% range) of the target dose. Subjects will be classified as "adherent" if they receive at least 80% of the total dose of Zepatier. Subjects who receive less than 80% of the total dose of Zepatier will be classified as "non-adherent." Analyses using self-reported adherence will also be conducted. Self-report is more accessible to clinicians than pill count, and there is added value in performing analogous analyses using the self-report measure.

Because adherence will be measured two ways (pill counts and self-report) *concordance correlation coefficients* will be calculated and performed to evaluate agreement between the measures. We will also test if the means of the two measurements are equal. Because adherence will be measured monthly, mixed-effects linear models for repeated measures that account for within-subject correlation will be used. In addition, we will examine the adherence data using a dichotomous cut-off (adherence \geq 80%), and determine the proportion of subjects who were sometimes, always, or never adherent during the 12-week treatment period. To this end, separate analyses will be performed for pill count and self-report adherence data.

For subjects randomized to the a-DOT arm, association between active drug use during treatment and the continuous adherence will be tested using Student's t or Wilcoxon signed rank test, depending on normality of the data. Bivariate analysis of dichotomous adherence data with categorical variables will be performed with chi-square and Fisher exact tests. We will conduct multivariate logistic regression analyses based on findings from the univariate analysis, but recognize that our modest sample size will limit such models.

Based on our pilot data, if we conservatively assume that 80% of subjects in the a-DOT will achieve \geq 80% adherence (v. 50% in the TAU arm), we will have $>$ 80% power to find a statistically significant difference. With the application of mixed-effects logistic regression to the repeatedly measured binary adherence outcome, power will be greater than 80% no matter how large the within-subject outcome correlation or intraclass correlation (ICC).

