In our previous DOT study, mean adherence in the mDOT group was 87% (SD=12%, n=21), and mean adherence in the TAU group was 77% (SD=20%, n=19) which translates into a standardized effect size or Cohen's d = 0.6. Based on this effect size, the power of the mixed effects linear model for the repeatedly measured continuous adherence outcome will be greater than 80%, even if anticipated ICC is as high as 0.5.

We will determine the proportion (and Wald or exact 95% CI) of subjects randomized to aDOT arm (n=50) who achieve SVR. For example, if SVR is achieved in 70% of the 50 study participants, the 95% confidence interval around that proportion will be: 57%, 83%. If SVR is achieved in 80%, the 95% confidence interval will be: 69%, 91%. If SVR is achieved in 90%, the 95% confidence interval will be: 82%, 98%. The overall SVR for all subjects will be compared to historical controls to demonstrate feasibility of treating real-world injection PWIDs with Zepatier-based regimens. Although our study lacks power to definitively answer the question of whether a-DOT improves SVR, our study will provide an estimated effect size to be used in future R01-funded studies examining the efficacy of a-DOT.

We used power calculations for Fisher's exact test (with 80% power and 5% significance level in a two-tailed test) to find the minimum detectable difference between the percentage of "adherent" subjects in the favorable group (e.g. not actively using drugs) vs. unfavorable group (e.g. actively using drugs). We would be able to find that a characteristic is significantly associated with adherence if there are 71% "adherent" subjects in the favorable group vs. no more than 41% "adherent" subjects in the unfavorable group (3.55 in terms of odds ratio). When using adherence as a continuous measure, we will have greater power to show correlations between continuous predictor variables and adherence. We calculated the minimum detectable correlation coefficient with 80% power and 5% significance level to be 0.33 which represents a small to medium correlation effect size. Therefore, we expect to have sufficient power to detect some associations that are likely to exist.

We will determine an effect size with respect to the outcome of adherence in the aDOT + gamification arm vs. a-DOT arm which will inform future R01 interventions.

C. References

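### B.10 calls the 80% v 50% power assumption conservative, but it sits at or slightly above the pilot estimate, and a single two-sided comparison does not reach the stated >80% power

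*Combined protocol and SAP*

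**What the plan says.** B.10 (Analytic plan) introduces the planning rates for the dichotomous outcome (at least 80% adherence) as follows: "Based on our pilot data, if we conservatively assume that 80% of subjects in the a-DOT will achieve" the threshold, "v. 50% in the TAU arm". It claims more than 80% power for this difference. It then says that mixed-effects logistic regression on the repeated binary outcome keeps power above 80% whatever the ICC.

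The pilot is described in B.1.4. Its result on the same threshold is "adherence v. 53% in the TAU arm", with p=0.09. The mDOT percentage that should precede this is lost at a page break in the text available. That is a loss in reading the file and not a fault in the plan. The 81% printed just before the break is given there as an SVR rate and is not used below.

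The pilot's size appears twice. B.1.4 says "We have completed the study (n=80" in total. B.10 reports adherence as "mean adherence in the mDOT group was 87% (SD=12%, n=21), and mean adherence in the TAU group was 77% (SD=20%, n=19".

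**The concern.** An assumption called conservative tells the reader that the true effect is probably at least as large, and so that power is probably at least as high as stated. The one pilot figure that can be compared directly points the other way: 50% assumed in TAU against 53% observed. Lowering the control rate widens the gap and raises the calculated power.

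What is at stake is how far the >80% claim can be relied on. If the planning gap is no smaller than an imprecise, non-significant pilot difference, the claim has no margin built in and must stand on its arithmetic alone.

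**Working it through.** **Inputs.** Planning rates 80% and 50% (B.10). Pilot TAU 53%, p=0.09 (B.1.4). Pilot adherence arms 21 and 19 (B.10). Trial arms 25/25/25 (B.2), with the two a-DOT arms together making 50 (B.9.6), hence 50 v 25. Three pill-count visits, at weeks 4, 8 and 12 (Table 3). Two-sided 5% is an assumption: B.10 states it only for the drug-use comparison.

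**1. The plan's own figure.** Normal approximation: power = Φ[(Δ − 1.96·SE0)/SE1], with SE0 from the pooled rate and SE1 from the separate rates.
- Pooled rate = (50×0.80 + 25×0.50)/75 = 0.70
- SE0 = √[0.70×0.30×(1/50 + 1/25)] = 0.1122
- SE1 = √[0.80×0.20/50 + 0.50×0.50/25] = 0.1149
- Power = Φ[(0.30 − 0.2200)/0.1149] = Φ(0.696) = 76%

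Exact power sums the binomial probabilities of all tables with p ≤ 0.05. It gives 69% for Fisher and 77% for uncorrected chi-square. The stated >80% is not reproduced. At 25 v 25 the approximation gives 61%, so 50 v 25 is the more favourable reading.

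**2. The pilot gap.** 53% of 19 is 10/19. Trying each mDOT count out of 21 near the reported p-value:

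| mDOT | Rate | Gap (points) | Fisher p | Chi-square p | Yates p |
|---|---|---|---|---|---|
| 16/21 | 76% | 23.6 | 0.186 | 0.119 | 0.219 |
| 17/21 | 81% | 28.3 | 0.091 | 0.056 | 0.116 |
| 18/21 | 86% | 33.1 | 0.038 | 0.023 | 0.053 |

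Only 17/21 with Fisher's test rounds to 0.09. A gap above 30 points needs at least 18/21, and no test gives 0.09 there. So on these arm sizes the planning gap of 30 is slightly above the inferred pilot gap of 28.

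**3. Power at the inferred pilot rates, one outcome per subject.** At 81 v 53 the pooled rate is 0.7167, SE0 = 0.1104 and SE1 = 0.1142. Power = Φ[(0.28 − 0.2163)/0.1142] = Φ(0.557) = 71%. Exact power at 50 v 25:

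| a-DOT v TAU | Fisher | Chi-square |
|---|---|---|
| 80 v 50 (plan) | 69% | 77% |
| 81 v 53 (inferred pilot) | 64% | 72% |
| 80 v 53 | 60% | 69% |

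**4. Three repeated measures.** As an approximation, multiply each arm by 3/(1 + 2·ICC) and use the formula in step 1.

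| ICC | Multiplier | 80 v 50 | 81 v 53 |
|---|---|---|---|
| 0.5 | 1.5 | 90% | 87% |
| 0.75 | 1.2 | 83% | 79% |
| 1 | 1.0 | 76% | 71% |

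At ICC 1 the extra visits add nothing and power falls back to the single-measure value. The claim of more than 80% at any ICC therefore fails on both sets of rates.

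**The case against.** The best defence is that the plan is close to its pilot. The word *conservatively* attaches most directly to the 80% for a-DOT, which is a point below the inferred 81%. Only the TAU rate was rounded the favourable way, and the net excess is under 2 points. The planned repeated-measures model would still have about 87% power at the inferred pilot rates with ICC 0.5, the value that B.10 treats as high for the continuous outcome. All of this stands. It rules out calling the assumption clearly optimistic, but it does not make it conservative.

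A one-sided test at 50 v 25 would give 84% at 80 v 50. B.10 does not say that this comparison is one-sided.

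A reader might infer three stronger points that the documents do not support.
- *The pilot gap was only about 20 points, because the pilot had 80 subjects.* With TAU at 53%, no split of 80 into arms of 36 to 44 gives p=0.09 by Fisher, chi-square or Yates, and B.10 reports the adherence data on 21 + 19.
- *TAU adherence will be higher here.* The pilot control was "standard DOT with weekly provider-administered IFN and self-administered ribavirin for improving adherence", and a once-daily tablet may be easier to take. But this trial also requires recent illicit drug use (Table 1) and recruits from a shelter and a syringe exchange, which may lower it. The documents give no figure either way.
- *A null result will be read as evidence against a-DOT.* The plan never calls its effect a lower bound, and B.9.5 describes the study as a pilot.

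**Conclusion.** The point holds in a limited form. The pilot does not support calling 80% v 50% conservative. The assumed TAU rate is 3 points below the printed pilot rate, and the 30-point gap is at or slightly above a pilot estimate of about 28 points that was not itself significant. For a single binary comparison at 50 v 25, two-sided 5%, power is 69% (Fisher) or 77% (chi-square) on the plan's rates and 64% or 72% on the inferred pilot rates, so the >80% claim is not met on either. For the repeated-measures model it holds at moderate ICC and fails as ICC approaches 1.

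This rests on four assumptions: the pilot p-value came from Fisher's test on 21 and 19 subjects; the two a-DOT arms are pooled; testing is two-sided; and the repeated-measures figures, which are approximate, apply the same rates at every visit. The comparison of 50% with 53% needs none of them.

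**What to change.** In B.10, delete *conservatively*. Give the pilot's mDOT and TAU proportions with their denominators, and base the calculation on them. Name the arms compared, the test and the sidedness. Replace the >80% claim with two sets of figures: power for the single comparison, and power for the mixed-effects logistic model over a stated ICC range, without the assurance that it holds at any ICC.

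Higher TAU rates can be added if labelled as sensitivity scenarios and not as pilot findings. For example, with a-DOT at 80%, exact power at 50 v 25 (Fisher / chi-square) is 38% / 46% for TAU at 60% and 23% / 30% for TAU at 65%.

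The cost is protocol wording and a small table. No design change is needed, but the stated power becomes less favourable.

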Automated DOT (a-DOT), a smartphone app that uses facial recognition software and advanced features to detect noningestion, combines the accuracy of in-person DOT with the convenience of real-time centralized data collection and monitoring. Adding a daily side effect diary to a-DOT will further allow precise tracking of timing of both medication ingestion and side effects which may be compromising adherence. Zepatier (elbasvir and grazoprevir) is a new once-daily fixe-dose combination tablet which has achieved high rates of SVR ranging from 94 to 97 percent in genotype-1 infected patients including those with HIV/HCV coinfection and renal impairment. Zepatier is administered for 12 to 16 weeks, depending on HCV genotype, prior treatment history, and the presence of certain baseline NS5A polymorphisms (1a only). By administering Zepatier via this innovative a-DOT platform, we hypothesize that PWIDs treated in real-wrold settings can be successfully treated with high rates of adherence and SVR.

In this proposed 18-month trials, 75 PWIDs enrolled in opiate agonist treatment (genotypes 1a and 1b) with chronic HCV will be enrolled over a 12-month period, and randomized to either aDOT or treatment as usual (TAU). **We will recruit PWIDs from diverse community settings include a syringe exchange program (NYHRE), federally-qualified health center (Comprehensive Health Care Center), homeless shelter (The Living Room), and a methadone maintenance treatment program (Montefiore Wellness Centers).** All patients (including treatment-experienced and HIVV/HCV coinfectd subjects) will be treated with Zepatier-based regimens as per the standard of care. Rigorous data are necessary to judge the contribution of a-DOT to the success of HCV treatment in PWIDs. By performing a randomized trial of a-DOT HCV therapy (Zepatier with and without ribavirin), we will evaluate the efficacy of a-DOT for improving HCV treatment outcomes among PWIDs.

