B.2. Overview of study approach. In the proposed study, 75 HCV-infected genotype-1 infected PWIDs eligible for on-site HCV treatment with Zepatier will be recruited from diverse community settings, and randomized to either aDOT (n=25), aDot + gamification (n=25), or TAU (n=25). We will measure adherence with pill counts in both arms and with the a-DOT interface in the a-DOT arm. All subjects will be treated with the standard regimens for 12 weeks based on subtype, baseline NS5a polymorphisms and treatment history. For this study we will not enroll patients taking Ribavirin.

- G1a: Treatment-naïve or PegIFN/RBV-experienced without baseline NS5A polymorphisms: Zepatier for 12 weeks
- G1b: Treatment-naïve or PegIFN/RBV-experienced: Zepatier for 12 weeks

B.3. Setting: Montefiore and Einstein Division of Substance Abuse (DoSA). DoSA is a clinical, research, and teaching division of Einstein’s Department of Psychiatry and Behavioral Sciences. DoSA operates a comprehensive substance abuse treatment program providing pharmacotherapy and related services to about 4200 adults (≥ 18 years) with current narcotic addiction (typically heroin). The primary focus is treatment of opiate dependence with methadone, and the average methadone pick-up schedule is 5 times per week. At present, DoSA operates three large clinics in three Bronx communities. The treatment paradigm relies on integrating general and HCV- and HIV-related medical, substance abuse, and mental health services under one roof. Multiple RCTs have been conducted in DoSA. Both recruitment and research visits will occur at DoSA. With [name] (HCV Medical Director), participant recruitment and private office space for research visits will be ensured. We have established treatment programs and/or partnerships with three additional programs: **syringe exchange program (New York Harm Reduction Educators - NYHRE), federally-qualified health center (Comprehensive Health Care Center), homeless shelter (The Living Room), and a methadone maintenance treatment program (Montefiore Wellness Centers).**

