B.9.6. Subject Compensation. Subjects will receive \$25 for each research visit and \$10 for each returned blister pack. Subjects randomized to the a-DOT arm (n=50) will receive additional incentives based on adherence measured at monthly visits: \$10 for 50% adherence; \$20 for 80% adherence; and \$30 for 95% adherence. For the subjects further randomized to the a-DOT + gamification intervention, the second-most adherent participant will receive an additional \$35 incentive, while the top-most adherent patient will receive a \$50 incentive at their subsequent study visit. Should the top two participants be tied, the participant with the most adherent time of dosing will be awarded the first-place prize. In total, participants may earn up to \$453, including metrocards and incentives.

B.9.7. Data Management/Confidentiality. Data will be stored with study ID codes in locked filing cabinets, separate from name-based files, which will be stored in a different locked cabinet. All study information and name-based information will be kept in separate, password protected, HIPAA compliant REDCap databases online. All name-based information will be destroyed at the end of the study, while study-ID-based information will be deleted if participants decline to allow storage of their records for future research of 50 years. All participants will be informed of the data management and confidentiality plan at the time of consent to participate.

B.10. Analytic plan.

First, the success of randomization will be checked by comparing the a-DOT and TAU groups on key variables, such as age, gender, race, HCV viral load, advanced liver disease, psychiatric, and active drug use. Continuous variables will be compared between study arms using the Student's t or Wilcoxon test, and

categorical variables will be compared using chi-square or Fisher's exact tests. Variables that are not equally distributed will be included in multivariate models if they are also associated with the study outcome.

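### The B.10 claim of more than 80% power for 80% v 50% adherent, at any ICC, does not hold for 50 a-DOT v 25 TAU subjects at two-sided 5%

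*Combined protocol and SAP*

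**What the plan says.** B.10 defines adherence once per subject over the first 12 weeks: a subject is adherent "if they receive at least 80% of the total dose of Zepatier". It also plans mixed-effects models for the monthly measurements.

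The power statement begins "if we conservatively assume that 80% of subjects in the a-DOT will achieve" the 80% adherence threshold, against 50% in TAU, and claims power above 80%. For mixed-effects logistic regression on the repeated binary outcome it then says that "power will be greater than 80% no matter how large the within-subject outcome correlation or intraclass correlation (ICC". No sample size per group, alpha, sidedness, number of visits or ICC scale is attached to either claim.

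On group sizes, B.2 has subjects "randomized to either aDOT (n=25), aDot + gamification (n=25), or TAU (n=25". B.9.6 and B.10 pool the two app arms: "Subjects randomized to the a-DOT arm (n=50) will receive additional incentives" and "subjects randomized to aDOT arm (n=50) who achieve SVR". The introduction still describes two groups, "randomized to either aDOT or treatment as usual (TAU".

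**The concern.** The second claim depends on the first. When outcomes within a subject are perfectly correlated, three visits carry no more information than one. Power can therefore exceed 80% at every ICC only if it exceeds 80% with a single outcome per subject. With 25 subjects in the smaller group, that is doubtful for a difference of 30 percentage points.

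Aim 1 asks whether a-DOT improves adherence, so this is the power statement for a main comparison. A reader would take the chance of missing the assumed effect to be below 20%, for the subject-level comparison as well as for the repeated-measures model. A non-significant result would then be judged against a power that the design does not have.

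**Working it through.** **Inputs**

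- Adherent rates: 0.80 a-DOT, 0.50 TAU (B.10).
- Group sizes: 50 v 25 (B.2; pooled a-DOT in B.9.6 and B.10).
- Alpha: two-sided 5%. This is an assumption. B.10 states it only for the later calculation on drug use and adherence.
- Visits: three, at weeks 4, 8 and 12 (Table 3), with exchangeable correlation assumed.

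**One outcome per subject, 50 v 25**

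Pooled rate = (50 × 0.80 + 25 × 0.50)/75 = 0.70.

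SE under no difference = √[0.70 × 0.30 × (1/50 + 1/25)] = 0.1122.

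SE under the alternative = √(0.16/50 + 0.25/25) = 0.1149.

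Power = Φ[(0.30 − 1.96 × 0.1122)/0.1149] = Φ(0.696) = 75.7%.

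With the unpooled SE throughout: Φ(0.30/0.1149 − 1.96) = 74.3%. By exact enumeration, Pearson chi-square gives 76.8% and Fisher 69.1%. Other two-sided variants (arcsine, log odds ratio, likelihood ratio, mid-p, continuity-corrected) run from 66.8% to 75.1%. None reaches 80%.

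**Can the stated figure be reproduced another way?**

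| Reading | Normal approximation | Fisher |
|---|---|---|
| 50 v 25, two-sided 5% | 75.7% pooled, 74.3% unpooled | 69.1% |
| 50 v 25, one-sided 5% | 84.2% pooled | 76.7% |
| Two arms, 37 v 38, two-sided 5% | 78.9% pooled, 81.9% unpooled | 75.0% |
| a-DOT alone v TAU, 25 v 25, two-sided 5% | 60.9% pooled, 64.9% unpooled | 51.0% |

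Only a one-sided test, or a two-arm split with the unpooled formula, exceeds 80%.

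**Difference detectable at 50 v 25.** 80% power needs about 81.5% v 50% by the pooled formula and about 82% by the unpooled one. By Fisher it needs about 83.5% (79.3% power at 83%, 80.9% at 83.5%).

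**Repeated binary outcome, observed-scale ICC.** With three visits, each variance above is multiplied by (1 + 2 × ICC)/3.

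| ICC | Pooled | Unpooled |
|---|---|---|
| 0 | 99.5% | 99.5% |
| 0.5 | 90.0% | 89.2% |
| 0.8 | 81.3% | 80.1% |
| 0.9 | 78.5% | 77.1% |
| 1 | 75.7% | 74.3% |

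Power crosses 80% at an ICC of 0.846 (pooled) or 0.803 (unpooled).

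**Fitted random-intercept logistic model.** This was simulated with three visits, marginal rates of 80% v 50%, a likelihood-ratio test for arm and 5,000 runs (Monte Carlo SE about 0.3 to 0.6 points). At 50 v 25 with no dropout, power is 93.4%, 87.1%, 82.1%, 80.4% and 79.3% at latent-scale ICC of 0.5, 0.8, 0.95, 0.97 and 0.99. A latent ICC of 0.95 corresponds to about 0.78 to 0.80 on the observed scale, so the two calculations agree.

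**Illustrative loss of 8%.** B.6 cites 92% follow-up in an earlier trial; applied equally to both groups it leaves 46 v 23. One outcome per subject then gives 72.2% (Fisher 65.7%). The observed-scale ICC limit falls to 0.70 to 0.74, and the fitted model gives 84.2%, 81.5% and 78.1% at latent ICC of 0.8, 0.9 and 0.95.

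**The case against.** - **The any-ICC sentence concerns the mixed model, which does well.** This largely stands. With no dropout the simulated model stays above 80% up to a latent ICC of 0.97. The 79.3% at 0.99 is only about 1.2 Monte Carlo SEs below 80%, so on its own it does not show a shortfall. The limiting argument does not depend on that simulation: at an ICC of 1 the data reduce to one outcome per subject.
- **The inputs are unstated, so the figure may rest on a one-sided test or a two-arm split.** This is possible, and the introduction's two-group wording makes a leftover figure plausible. But the only sidedness that B.10 gives is two-tailed, and the allocation in B.2 is three-arm. If either reading was the basis, it needs to be stated and reconciled.
- **Fisher is given too much weight.** B.10 says "Bivariate analysis of dichotomous adherence data with categorical variables will be performed with chi-square and Fisher exact tests", in a paragraph that opens with the a-DOT arm and drug use, so it does not clearly prescribe Fisher for a-DOT v TAU. The Fisher figures are therefore secondary. The chi-square figure, 76.8%, still falls short.
- **The 8% loss is borrowed.** It comes from 24-week follow-up in another trial, and B.9.3 gives rules for packs that are not returned. It is an illustration only, and the conclusion does not need it.
- **This is a pilot.** B.9.5 says so, and B.10 disclaims power for SVR. It makes no such disclaimer for adherence, where it claims power outright.

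**Conclusion.** The concern holds. For 80% v 50% adherent at 50 v 25 and two-sided 5%, single-outcome power is about 76%, not above 80%, and the assurance at any ICC is therefore false. The chance of missing the assumed effect is about 24% (31% by Fisher) rather than under 20%. The shortfall is modest: about 4 points, or 11 by Fisher.

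The planned repeated-measures analysis is adequately powered at moderate ICC. The fault lies in the single-outcome figure and the unconditional wording, not in the choice of model.

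The conclusion assumes a two-sided 5% test and the pooled 50 v 25 contrast. If a-DOT alone v TAU was meant, the gap is much larger (61%; Fisher 51%).

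**What to change.** In B.10:

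1. Restate the single-outcome power. Suggested wording: With 50 a-DOT subjects (both a-DOT arms pooled) and 25 TAU subjects at two-sided 5%, power is about 76% (69% by Fisher's exact test) for 80% v 50% adherent; 80% power requires about 81.5% v 50%. If a-DOT alone v TAU is intended, state about 61%.
2. Delete the clause that extends the claim to any ICC. Replace it with power from the planned mixed-effects logistic model over a stated ICC range, giving n per group, alpha and sidedness, number of visits, ICC scale and allowance for dropout.
3. If a one-sided test or a two-arm split was the basis, say so and reconcile it with the three-arm design.
4. For clarity only, state that the claim of more than 80% power for continuous adherence refers to the pooled 50 v 25 contrast. It holds there: about 84% at d = 0.6, ICC 0.5 and three visits.

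The cost is wording plus one power run. No extra patients are needed and the analysis does not change. The stated power becomes slightly less favourable.

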
Initial screening visit and informed consent:
 
 • Obtain oral consent for brief screening using Einstein Committee on Clinical Investigations (IRB) screening consent template • Brief screen in private room in clinic to determine eligibility • Discuss study procedures, risks and benefits of study participation • Obtain written consent for 1) clinical trial participation; 2) study staff to use protected health information from methadone clinic records; 3) study staff to disclose protected health information in event of psychiatric distress

HCV clinic chart review:
 
 ▪ Laboratory test results: HCV Ab, HCV viral load, HIV, HCV genotype/subtype, IL28B, APRI and FibroSURE (biomarker tests for liver fibrosis), absence of advanced cirrhosis (labs within 3 months - bilirubin, albumin, PT/INR), CBC, PT/INR, AFP, ANA, and GFR (for obese patients – adjusted GFR) • Methadone or buprenorphine dose if applicable

Second screening visit (medical and psychiatric eligibility):
 
 ▪ Review of HCV-related labs (as above) and staging by liver biopsy/fibroscan (if available) ▪ Review of HCV Treatment Evaluation Flow Sheet to confirm planned on-site treatment regimen: Zepatier with or without ribavirin as per 2016 AASLD/IDSA HCV guidelines ▪ Participants who meet all eligibility criteria scheduled for a baseline visit

B.6. Participant tracking and retention. We have extensive experience following HCV- and HIV- infected drug users in studies. In our completed RCT of directly observed HCV treatment, 24-week follow-up was 92%. In our completed RCT of directly observed HAART, 24-week follow-up was 86%. At enrollment and subsequent visits, we will record: 1) participants’ address, phone number, and social security number; 2) contact information of family or friends; 3) contact information of participants’ community-based organizations; 4) contact information of case managers; and 5) locations where participants “hang out”.

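### The claim of over 80% power for continuous adherence needs d=0.6 to be a single-visit effect; if the pilot SDs are of per-subject averages, as they appear to be, power is about 68% for 50 v 25

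*Combined protocol and SAP*

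**What the plan says.** Section B.10 gives the pilot result as "mean adherence in the mDOT group was 87% (SD=12%, n=21), and mean adherence in the TAU group was 77% (SD=20%, n=19"), and says that this "translates into a standardized effect size or Cohen's d = 0.6". From that effect size it concludes that the "power of the mixed effects linear model for the repeatedly measured continuous adherence outcome will be greater than 80" per cent, "even if anticipated ICC is as high as 0.5".

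The model is described earlier in B.10: "Because adherence will be measured monthly, mixed-effects linear models for repeated measures that account for within-subject correlation will be used". The same section also defines continuous adherence as a single percentage per patient of the target dose over the first 12 weeks.

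For this calculation the plan does not give the scale of the pilot SDs (single visit or average over treatment), the number of repeated measures, the contrast (50 v 25 or 25 v 25), alpha or dropout.

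**The concern.** A repeated-measures analysis gains power because averaging several visits removes part of the within-subject variation. The gain is real only if the SD used to standardise the effect is the SD at one visit. If that SD already describes one averaged value per subject, the within-subject part has already been reduced, and a further ICC-based reduction counts the same gain twice.

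The plan's wording shows that a gain was applied. The remark about the ICC makes sense only if power falls as the ICC rises, which is how a single-visit effect size behaves under averaging.

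The pilot figures, however, look like per-subject summaries:

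- B.10 reports one mean, one SD and one n for each pilot group.
- B.1.4 reports the pilot by the share of subjects reaching 80% adherence, with 53% in TAU; 10/19 = 52.6%.
- B.10 defines this trial's own continuous measure as one 12-week percentage per patient.

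The figure matters because Aim 1 tests adherence and SVR, and B.10 concedes that the study lacks power for SVR. Adherence is therefore the outcome on which a power claim is made. If power is nearer two-thirds than four-fifths, a non-significant adherence result is weaker evidence against a-DOT than a reader of B.10 would suppose.

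**Working it through.** **Inputs.** Pilot 87% (SD 12, n=21) v 77% (SD 20, n=19), d=0.6 and ICC up to 0.5 are from B.10. Arms of 25/25/25 are from B.2, and the pooled a-DOT group of 50 is from B.9.6 and B.10. Three monthly counts (weeks 4, 8, 12) are from Table 3. B.9.3 speaks of 6 to 8 observation periods, so six biweekly packs over 12 weeks is the alternative. Two-sided 5% is stated in B.10 for the Fisher calculation and is assumed here. No dropout is applied.

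**Effect size.** Pooled SD = √[(20×12² + 18×20²)/38] = √(10,080/38) = 16.29. d = 10/16.29 = 0.614, which the plan rounds to 0.6.

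**Formulae.** For the mean of m equally correlated visits, the variance factor is VF(m) = [1 + (m−1)×ICC]/m. With balanced data the average between-arm effect in a linear mixed model is in effect tested on subject means. Power therefore comes from a noncentral t with noncentrality (d/√VF)×√[n₁n₂/(n₁+n₂)]. For 50 v 25 the last term is √(1250/75) = 4.082; for 25 v 25 it is √(625/50) = 3.536.

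**Step 1: reproduce the plan's figure (d=0.6 as a single-visit effect).** With m=3 and ICC 0.5, VF = (1 + 2×0.5)/3 = 0.667. The noncentrality is (0.6/√0.667)×4.082 = 3.00, and power is 84%. With m=6 it is 89%. The stated figure therefore reproduces for 50 v 25.

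**Step 2: d=0.6 as a subject-average effect, same number of counts in pilot and trial.** VF = 1, the noncentrality is 0.6×4.082 = 2.45, and power is 68%. With d=0.614 it is 70%. The effect detectable with 80% power is d=0.695 (0.70 rounded), and 0.695×16.29 = 11.3 points, against the 10 points assumed.

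**Step 3: pilot and trial average different numbers of counts.** If the pilot averaged p counts and the trial uses m, the relevant factor is VF(m)/VF(p). Occasions are taken to have equal variance (an assumption).

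| Pilot counts averaged | Trial counts | Factor at ICC 0.5 | Power, 50 v 25, d=0.6 |
|---|---|---|---|
| 1 | 3 | 0.667 | 84% |
| 2 | 6 | 0.583/0.750 = 0.778 | 78% |
| 3 | 6 | 0.583/0.667 = 0.875 | 73% |
| equal | equal | 1 | 68% |
| 6 | 3 | 0.667/0.583 = 1.143 | 62% |

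**Step 4: the 25 v 25 contrast at d=0.6.** On the single-visit reading with three visits and ICC 0.5, power is 72% (78% with six counts). On the subject-average reading it is 55%.

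**Check on the scale of the pilot data.** Fisher's exact test of 17/21 v 10/19 gives p=0.091, which agrees with the p=0.09 printed in B.1.4; 16/21 gives 0.19 and 18/21 gives 0.04. The mDOT percentage is lost at a page break, so 17/21 is inferred. The result fits one adherence value per subject in a 21 v 19 data set, but does not show how that value was formed.

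**The case against.** The strongest objection is that no section states the scale of the pilot SDs. An SD across subjects at a single visit would also be reported with n equal to the number of subjects, and an 80% cut-off at one occasion would give the same 2×2 table. If d=0.6 is a per-visit effect, the plan's sentence is right for 50 v 25. B.1.4 is also imperfect evidence, since it describes the completed pilot as n=80 with 88% v 77%, whereas B.10 uses 40 subjects and 87% v 77%. This stands, and it is why the conclusion is conditional.

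Three stronger readings are tempting, and the documents do not support them:

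- **That the plan has certainly made an arithmetic error and true power is 60–70%.** This treats the averaged scale as established. It is the natural reading, but an inference.
- **That repeated visits can add nothing.** If the pilot averaged fewer counts than this trial collects, some gain is real. With 2 pilot counts and 6 trial counts, power is 78% at ICC 0.5 and 86% at ICC 0.3.
- **That the pilot averaged six monthly counts over 24 weeks.** The only hint is "In our completed RCT of directly observed HCV treatment, 24-week follow-up was 92" per cent in B.6, which is a retention figure and gives no counting schedule.

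It is also fair to say that B.9.5 calls the study a pilot and that the 75 subjects are not shown to come from this calculation. That limits the consequences. It does not justify an explicit power figure whose key input is undefined.

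**Conclusion.** The point holds in conditional form. The stated power of over 80% at ICC 0.5 requires the contrast to be pooled 50 v 25 and d=0.6 to be essentially a single-visit effect. Neither is stated for this calculation, and the evidence in the documents is against the second. If the pilot SDs are of per-subject averages over a comparable number of counts, power is about 68% (70% at d=0.614), and the difference detectable with 80% power is about 11.3 points. Unequal numbers of counts move this figure; at ICC 0.5 it is 73% for three pilot counts and six trial counts, and 62% for the reverse. For 25 v 25, power at ICC 0.5 is below 80% on either reading.

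These results assume two-sided 5%, a common SD, equal variance and correlation across occasions, and no dropout. The sentence needs repair on either reading, because the reader cannot tell from it which calculation was done.

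**What to change.** In B.10, state the scale of the pilot SD, the number of repeated measures per subject, the contrast (50 v 25 or 25 v 25) and alpha. Take a per-visit SD and an ICC from the pilot's repeated counts, and recompute power from those.

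If only the per-subject SD is available, replace the claim of over 80% and its ICC clause with wording such as: *about 68% at d=0.6 for 50 v 25; 80% power requires a difference of about 11 points*. Apply no ICC reduction to that SD.

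The cost is a change of protocol wording and a less favourable power statement. Patients and procedures are unaffected.
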